improvement toolkits that are common to both intervention conditions to all agencies/programs. Each conference is followed by planning and training for the intervention condition, followed six months later by client screening and recruitment of depressed patients into a panel study with baseline and 6- and 12-month measures. Administrators in all agencies and clinicians in sites participating in the trial, as well as some sites not in the trial, will complete an 18 month follow-up survey. After several months of collaborative analysis involving community agency partners, the project will sponsor a community feedback conference to share the outcomes findings and provide assistance in use of intervention materials based on evidence for their effectiveness. Final analyses and feedback conference will occur in the last year of the study.

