Appendix A

This report provides information on detailed technical methods for handling of issues for the analysis of 6-month client data as well as 12-month and 3 years follow-ups.

Table of Contents		Page
A1	Analytic Sample	A-2
A2	Weighting	A-3
A3	Multiple Imputation	A-4
A4	Analyses	A-6
A5	References for Appendix	A-10

A1. Analytic Sample

Enrollment

The study settings were South Los Angeles and Hollywood-Metro. Participant sampling (program and client recruitment) and randomization are described in greater detail in prior publications. Within enrolled programs, clients were screened for eligibility in waiting rooms (consecutive selection) or events (random selection) between March 2010 to November 2010 by community members blinded to intervention condition and supervised by RAND. Staff approached 4,645 adults (age \geq 18) over 2-3 days per program; 4440 (96%) agreed to screening. Study eligibility was limited to clients providing contact information and depressed based on a score of 10 or greater on a modified 8-item Patient Health Questionnaire (PHQ-8) (3). Of 4,440 screened, 1,322 (30%) were eligible and 1246 (94%) consented. In our previous publications,(1-3) we created enrollment weights based on propensity weighting adjustment, by fitting logistic regression models to predict the enrollment among those eligible. The reciprocal of the predicted response probability was used as the enrollment weight for each participant. See Supplementary Materials in publications. ¹⁻⁵

Telephone survey

Baseline survey. Between April 27, 2010-January 2, 2011, we approached 1,246 consented clients for baseline telephone survey conducted by survey staff blinded to intervention condition and 981 clients (79% of 1246 consented, RS: 492, CEP: 489) completed the baseline, 36 refused (RS: 17, CEP: 19), 227 were unable to contact (RS: 96, CEP: 131), and 2 deceased (RS: 1, CEP: 1).

6 month follow-up survey. Between November 2, 2010 and August 11, 2011, we approached 1093 participants (RS: 540, CEP: 553) for 6-month follow-up telephone survey; 153 enrolled participants were excluded from the contact list because their baseline survey response status was in one of following categories: final refusal, ill or incarceration, unable to contact, or deceased. Of 1093 attempted for 6-month follow-up, N=759 (69% of attempted, RS: 380, CEP: 359) completed the survey, 12 refused (RS: 3, CEP: 9), 321 were unable to contact (RS: 157, CEP: 164), and 3 deceased (RS: 1, CEP: 2).

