Enrollment The enrollment weight was intended to make the enrolled sample (n=1,246) representative of a specific target population.^{6,7} That target population was defined as people who were: age 18 or older, visited a participating CPIC sites during our screening window, screened positive for PHQ-8, and provided contact information. We created enrollment weights based on propensity weighting adjustment, by fitting logistic regression models to predict the enrollment among those eligible. The reciprocal of the predicted response probability was used as the enrollment weight for each participant. Five versions of the enrollment weight were created corresponding to five imputed screener data, because imputed predictors from the

screeener data were used in fitting logistic regressions. Common predictors of age, community, and type of programs were used in all models.

Attrition The analytic sample for 6 months is comprised of 1,018 participants who completed baseline, or 6-month telephone follow-up surveys. We used nonresponse weighting to address missing data for subjects who did not who did neither complete baseline nor 6 months follow-up telephone surveys. We started with a large set of independent categorical variables to be considered for a logistic regression on the outcome of response among enrolled participants. The final model included predictors that were significant ($p < 0.05$) for either intervention arm (age, gender, ethnicity, living situation, income, US born), as well as for two design variables (community and sector of the screening program). The final weights defined on the analytic sample were the product of the two adjustment factors for enrollment and nonresponse. See Supplementary Materials in publications. We applied the weights to the 36-month outcome analysis excluding 24 deceased cases (1,004 attempted - 24 deceased = 980). The weights for 3-year main analysis defined on the analytic sample were the product of the two adjustment factors for enrollment and nonresponse. See Supplementary Materials in previous publications.¹⁻³

For 4-year follow-up, we tested bivariate associations between an indicator for responding at the 4-year survey and demographic and clinical characteristics at baseline and 3 years.⁵ The weighting model to predict follow-up status from 3-year sample included screener sector, age, education, working for pay, PCS-12, poor mental health-related quality of life at baseline, and risk for homelessness at 3 years.

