We conducted a longitudinal sensitivity analysis using all waves of data (baseline, 6-months, 12-months, 3-years) without response weights, adjusting for baseline covariates as in the primary analysis. We specified a spline model, with a linear segment between baseline and the first follow-up for initial improvement and another linear segment for the subsequent follow-ups; the two linear segments were specified to join at the first follow-up. In analyzing continuously scaled PCS-12 as the dependent variable, we used a 3-level, mixed-effects regression model by using SAS PROC MIXED. To account for the intraclass correlation due to the multilevel structure, we specified random effects at the program level and a spatial power covariance

structure at the client level to account for unequal spacing of waves. Initial explorations of 3-level, random-effects logistic models using SAS PROC GLIMMIX for binary outcomes yielded unstable estimates for program-specific random effects. We utilized a generalized estimating equation (GEE) framework with logistic regression models for binary outcomes and Poisson models for counts using SAS PROC GENMOD, specifying exchangeable correlation at the program level. From the estimated spline models, we developed a contrast involving a linear combination of coefficients to test intervention effects at each end point (baseline, 6-months, 12-months, and 3-years) and tested differences between intervention groups in change from baseline to 6 months, 12 months, and 3 years.

Exploratory analyses. The CPIC study had 2 primary outcomes: poor MHRQL (12-item mental health composite score, MCS-12 \leq 40), and depressive symptoms (PHQ-8 \geq 10 or PHQ-2 $<$ 3 for 4-year follow-up); and a community-prioritized outcome of mental wellness (a response of at least “a good bit of the time” in the previous 4 weeks to feeling calm or peaceful, having energy, or being happy), based on community input matched to the 36-item short-form health survey quality-of-life items. We developed 2 indicators: “clinical remission” (PHQ-8 $<$ 10 or PHQ-2 $<$ 3) and, with stakeholder input, “community-defined remission” (PHQ-8 $<$ 10 or PHQ-2 $<$ 3 or MCS-12 $>$ 40 or any mental wellness). We also used a count of survey periods in remission from baseline up to 3-year follow-up. Intervention status was the client’s program assignment at enrollment to CEP or RS.

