For time (survey period) to first remission, we used Cox proportional hazard models for the full sample with any survey data (n = 1018), limited to those at risk for subsequent clinical (n = 995) and community-defined (n = 408) remission at baseline. We used linear regression for number of periods in remission during the course of 3 years for the full sample (n = 1018). We developed models including intervention status, adding social determinants, then depression treatment.⁵

Analyses for 4-year outcome:

We conducted intent-to-treat analyses with intervention status as the main independent variable, using logistic regression for probability of remission (clinical, community-defined) for the sample with 4-year data (n = 298). We conducted analyses parallel to the 3-year analyses noted previously, using the same covariates plus base-line measure of the outcome and the 1 baseline item differing by intervention status among 4-year completers.⁵

A5. References

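### The exploratory count of survey periods in remission starts at baseline and is modelled without a stated baseline-remission covariate, which costs precision for community-defined remission

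*Combined protocol and SAP*

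**What the plan says.** Appendix A4, Exploratory analyses, defines two remission indicators, clinical and community-defined, and then a summary across waves: "We also used a count of survey periods in remission from baseline up to 3-year follow-up". The model is given a few lines later: "We used linear regression for number of periods in remission during the course of 3 years for the full sample (n = 1018".

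The restriction to clients not yet in remission applies to the Cox models only, which were "limited to those at risk for subsequent clinical (n = 995) and community-defined (n = 408) remission at baseline". The covariates are described in one sentence: "We developed models including intervention status, adding social determinants, then depression treatment". Baseline remission is not named.

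Elsewhere in Appendix A4 the baseline value is used. The 6-month models adjust for the baseline status of the dependent variable, the 3-year endpoint analysis controls for baseline, and the 4-year remission models are described as "using the same covariates plus base-line measure of the outcome".

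**The concern.** Appendix A4 treats baseline as one of the four survey waves (baseline, 6, 12 and 36 months), so on a plain reading a client already in remission at baseline scores one period before client follow-up starts. The arm difference in the four-wave count is then the baseline difference plus the follow-up difference. The first term adds variance and says little or nothing about remission during follow-up.

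The loss depends on how many clients are in remission at baseline. Clinical remission is nearly absent there by design, because eligibility required "a score of 10 or greater on a modified 8-item Patient Health Questionnaire (PHQ-8" or above-threshold status at screening. Community-defined remission is much broader, since it can also be met through the MCS-12 or any mental wellness item. At stake is the precision of the community-defined count, an exploratory outcome.

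**Working it through.** **Inputs from the documents.** The count model uses n = 1,018. Clients at risk of a first remission after baseline: 995 (clinical) and 408 (community-defined), Appendix A4. Two-sided alpha is 0.05 and design power 0.80 (section 5). The plan gives no power or effect figure for the count itself.

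**Baseline remission implied by the plan.**
- Clinical: 1,018 − 995 = 23, or 2.3%.
- Community-defined: 1,018 − 408 = 610, or 59.9%.

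These are upper limits if clients left the risk set for other reasons.

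**Chance imbalance at baseline.** Assume 509 per arm and no clustering. The SE of the difference in baseline proportions is √(p(1−p) × 4/1,018). The 95% range is ±0.060 periods for community-defined remission and ±0.018 for clinical. It passes undiluted into the unadjusted four-wave difference.

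**Precision, community-defined.** Assume prevalence 0.6 at every wave (v = 0.24), a common between-wave correlation r, and no clustering, weighting or other covariates.
- Four-wave count, unadjusted: variance = v(4 + 12r).
- Three follow-up waves, unadjusted: variance = v(3 + 6r).
- Three follow-up waves, adjusted for baseline remission: variance = v(3 + 6r − 9r²).

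| | r = 0.3 | r = 0.5 |
|---|---|---|
| Four waves (÷v) | 7.60 | 10.00 |
| Three waves (÷v) | 4.80 | 6.00 |
| Three waves, adjusted (÷v) | 3.99 | 3.75 |
| SE ratio, four vs three | √(7.60/4.80) = 1.26 | √(10/6) = 1.29 |
| SE ratio, four vs three adjusted | √(7.60/3.99) = 1.38 | √(10/3.75) = 1.63 |
| SE ratio, three vs three adjusted | √(4.80/3.99) = 1.10 | √(6/3.75) = 1.26 |

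**Power.** If the better analysis has 80% power, the worse one has Φ((1.960 + 0.842)/ratio − 1.960).
- Four vs three waves: about 61% (r = 0.3) and 58% (r = 0.5).
- Four vs three adjusted: about 53% and 40%.

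**Other assumptions.** Let follow-up prevalence run over 0.3-0.7, follow-up correlation over 0.3-0.5 and baseline-to-follow-up correlation over 0-0.5. Counting baseline then raises the SE by about 8-38% over an unadjusted follow-up count, and 80% power becomes 53-74%.

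**Clinical remission.** The baseline variance is 0.0226 × 0.9774 = 0.022. With follow-up prevalence 0.5 and correlation 0.3, the three-wave variance is 3 × 0.25 × 1.6 = 1.20. If baseline is uncorrelated with follow-up, variance rises by 1.8% and the SE by 0.9%. With baseline correlation 0-0.1 and the other ranges as above, the SE rises by 0.7-3.1% and power falls from 80% to 78-79%.

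**Why one covariate is enough.** Write the four-wave count as B + C, with B baseline remission and C the follow-up count. In a linear regression on arm and B, B is fitted exactly by itself and contributes nothing to the arm coefficient. The four-wave and three-wave counts therefore give the same arm coefficient, within each imputed dataset and after pooling.

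**The case against.** **The wording may mark only the window.** The phrase about baseline could mean the start of the period rather than a counted wave. That is possible, but the covariate is still missing on that reading, and the last ratio in the table (1.10-1.26) applies.

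**The covariate sentence is a short summary of published work.** It may not list everything. The 4-year sentence names the baseline measure as an addition to the shared covariates, which suggests that the earlier remission models lacked it but does not prove it.

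**Chance imbalance under randomisation is not bias.** Correct: it is already in the standard error. The point is lost precision.

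**The larger ratios combine two changes.** Also correct. Only 1.26-1.29 comes from counting the wave; the rest of 1.38-1.63 is the gain from adjustment. Social determinants in the model may absorb some variance, so the ratios lean towards upper limits.

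**Stronger readings that a reader might infer, and that the documents do not support:**
- *Baseline is cleanly pre-intervention.* Section 4 has planning and training "followed six months later by client screening and recruitment of depressed patients into a panel study". Baseline precedes client follow-up, but not the start of program-level activity.
- *At least 38 clients lack a 3-year value and are scored as not in remission.* The 3-year analysis set is "1,004 attempted - 24 deceased = 980", and 1,018 − 980 = 38. But the 1,004 is 1,246 − 8 deaths − 49 final refusals − 185 with no survey data, so the two sets are built differently. Appendix A3 imputes unit nonresponse at 3 years and exempts only the deceased. Deaths number at most 8 + 24 = 32, or 33 by the arm counts (RS 4 + 14 = 18, CEP 4 + 11 = 15), about 3% of 1,018. With 0.3-0.7 of the missing waves in remission, the difference of 3 deaths moves the arm difference by 3/509 × 0.3 to 3/509 × 0.7, or 0.002-0.004 periods.
- *The 3-year result is compromised.* The 3-year endpoint analysis is separate and controls for baseline.

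**Conclusion.** The point holds for one exploratory outcome, the community-defined remission count. As written, the count includes a wave at which up to 59.9% of clients already qualify, and no baseline adjustment is stated. The precision loss is material under the stated assumptions. The prevalence at follow-up, the correlations, the equal arms and the absence of clustering are assumptions; only the baseline rates come from the plan. For the clinical remission count the effect is negligible. No primary, community-prioritised or 3-year endpoint analysis is touched, so this is a worthwhile improvement and not a threat to the trial's conclusions.

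**What to change.** Add baseline remission (same definition as the outcome) as a covariate in the count model, and report the count over the 6-, 12- and 36-month waves so that its level is interpretable. State in Appendix A4 which waves are counted and how the few deaths are scored. There is no need to divide by the number of waves a client survived, which would change the estimand. The data are already collected, so the cost is one recode and a rerun of one exploratory model for each remission definition.

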With further 20% expansion, final	780	0.20-0.22	9.98-10.92%

†Detectable effect size (mean difference between two groups divided by the standard deviation)¹⁷⁸. §Detectable percentage point difference for two groups.

6. CPIC 3-Year extension (PCORI award # 1845)

Background: Depression is a leading cause of morbidity with disparities in care. Depression collaborative care, a team-based approach supporting care management, patient activation and evidence-based treatments, is effective relative to usual care but often unavailable in under-resourced communities. Community Partners in Care (CPIC) randomized 95 programs in healthcare and community-based (e.g., social services, faith-based) service sectors in two communities to Resources for Services (RS) for individual program technical assistance versus

Community Engagement and Planning (CEP) for multi-sector coalition support for depression collaborative care. For depressed clients, CEP relative to RS reduced having poor mental health-related quality of life (MHRQL) and behavioral health hospitalization over 6-12 months. Longer-term outcomes are unknown.

Aims: This extension study of CPIC aims to:

1. Compare CEP and RS effects at 3-year follow-up, 2-years after intervention support, on primary (depression and MHRQL), community-prioritized outcomes of physical health-related quality of life (PHRQL) and behavioral health hospitalization, and outpatient services use (secondary);
2. Compare effects of CEP and RS at 6, 12, and 36 months for CPIC participants enrolled in healthcare or community-based service sectors;
3. Describe outcome priorities for African American and Latino depressed clients, and as perceived by providers.
4. Describe views of stakeholders planning the Los Angeles County Health Neighborhood Initiative (HNI) informed by CPIC; and national stakeholders briefed on CPIC and HNI.

We hypothesized that CEP relative to RS would improve long-term mental and physical health and reduce hospitalization nights, overall and within sector. We expected stakeholders to prioritize social factors and mental health.

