Methods: Extension Study (Aims 1-3): Between 1/2014-10/2014, we approached 1004 CPIC clients initially screened as depressed from 89 programs and eligible for 3-year surveys; 600 participated (60%; RS 293, CEP 307). Aim 3: For client qualitative interviews, we approached 163 consecutive 3-year survey participants stratified by depression, race/ethnicity, gender and intervention; 104 participated (64%). For staff, we notified 289 completing 12 month surveys and used purposive follow-up stratified by community, service sector and intervention, to complete 51 interviews. Aim 4: We interviewed 49 county and community leaders planning HNI and 14 of 34 leaders attending a national briefing.

Data Sources: Self-report surveys (Aims 1 and 2) and semi-structured interviews (Aims 3 and 4).

Measures: Client outcomes are poor MHRQL ($MCS-12 \leq 40$) and depression ($PHQ-8 \geq 10$) (primary); PHRQL (12-item physical composite score (PCS-12), mental wellness, and behavioral-health hospitalization nights (community-prioritized); and use of outpatient services

(secondary). Clients and providers were asked about priorities for care and national stakeholders for responses to CPIC findings and related policy initiatives.

4-year follow-up of the 3-year sample (extension study).

The CPIC 4-year follow-up was added based on *community-stakeholder input that additional follow-up of the 3-year sample was desired to show longer-term effects on depression remission*. This follow-up built on the 3-year extension study as well as an opportunity to explore of using an existing funded cohort to recruit potential subjects into the Community and Patient Partnered Research Network (CPPRN).

Analyses plan: We will conduct 3-year end-status intent-to-treat analyses, and for 4-year follow-up of the 3-year sample, 4-year end status, with intervention status as the main independent variable, adjusted for baseline status and covariates, with response weights and multiple imputation (Aim 1); subanalyses of intervention effects within service sector at each follow-up (Aim 2); sensitivity analyses (raw data, longitudinal modeling and sector-by-intervention interactions); and thematic analyses of qualitative data (Aims 3 and 4)

7. Limitations

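### The exploratory Cox models for time to first remission run on survey-wave time but name no tie method or program-level variance, so the hazard ratio and its standard error depend on unstated options

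*Combined protocol and SAP*

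**What the plan says.** The models are in Appendix A, A4, in the part that opens "Exploratory analyses. The CPIC study had 2 primary outcomes".

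- **Time axis:** "For time (survey period) to first remission", so time is counted in waves.
- **Model and sample:** "we used Cox proportional hazard models for the full sample with any survey data (n = 1018"), then "limited to those at risk for subsequent clinical (n = 995) and community-defined (n = 408) remission at baseline".
- **Waves:** the 3-year longitudinal sensitivity analysis in A4 is described as "using all waves of data (baseline, 6-months, 12-months, 3-years) without response weights". The companion remission measure has the same reach: "We also used a count of survey periods in remission from baseline up to 3-year follow-up". The horizon of the Cox models is not given.
- **Not stated for the Cox models:** tie handling, a grouped-time form, clustering, a robust variance, or weighting.

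Elsewhere the plan does address clustering. Section 5 undertakes to account for the group-randomized design and for clustering within programs. A4 states clustering for the 6-month models, refers the 3-year endpoint analysis back to that strategy, and gives program-level random effects or exchangeable correlation for the 3-year longitudinal models. None of these statements names the Cox models.

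**The concern.** Remission is observed only at an interview, so many clients share each recorded event time. With 995 at risk and an assumed 20-50% remitting at the first wave, 995 x 0.20 = 199 to 995 x 0.50 = 498 clients would be tied there. The common forms of the Cox partial likelihood handle ties differently. With few ties the choice hardly matters; with ties of this size it can change the reported hazard ratio.

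Separately, programs were randomized, not clients. A model-based Cox variance treats clients as independent. If nothing is added for programs, the test may reject too often.

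At stake is how far the remission comparison can be read. Remission was defined with stakeholder input, and longer-term remission is the reason Section 6 gives for the 4-year follow-up.

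**Working it through.** **1. The plan's own clustering figures.** The documents give no power, event count or hazard ratio for the Cox models. The nearest stated figure is the last row of Table 4 (N = 780, ICC 0.00-0.02). With d = (t[0.975] + t[0.80]) x 2/sqrt(N) x sqrt(VIF) and VIF = 1 + (m - 1) x ICC:

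- ICC 0, df = 778: d = 0.201, or 9.98 points.
- ICC 0.02, 80 programs, df = 78: d = 0.220, or 10.92 points.

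Both match Table 4, so the same VIF formula and ICC range are used below.

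**2. Effect of the tie method.** Assumptions, none from the documents: equal arms, true proportional hazards with HR = 1.50, three waves, no loss to follow-up, and control-arm remission probabilities h per wave as listed. The treated probability at a wave is 1 - (1 - h)^1.5. The table gives the value each estimator approaches in large samples.

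| h at waves 1/2/3 | Breslow | Efron | Exact-discrete (odds scale) |
|---|---|---|---|
| 10/10/10% | 1.462 | 1.499 | 1.541 |
| 20/20/20% | 1.422 | 1.496 | 1.590 |
| 30/20/30% | 1.390 | 1.492 | 1.635 |
| 40/30/40% | 1.348 | 1.483 | 1.707 |
| 50/50/50% | 1.293 | 1.465 | 1.828 |

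With equal wave hazards the exact-discrete value is simply an odds ratio. At 20%, 1 - 0.8^1.5 = 0.284 and (0.284/0.716)/(0.20/0.80) = 1.59. At 50%, 1 - 0.5^1.5 = 0.646 and (0.646/0.354)/1 = 1.83. A complementary log-log model with wave intercepts returns 1.50, because log(-log(1 - p)) shifts by exactly log HR at every wave.

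On the log scale, Breslow keeps ln 1.422/ln 1.5 = 87% at 20% per wave and ln 1.293/ln 1.5 = 63% at 50%. Efron keeps 99% and 94%.

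**3. Standard error if programs are ignored.** Section 6 gives two program counts: the trial "randomized 95 programs in healthcare and community-based" sectors, and at 3 years "we approached 1004 CPIC clients initially screened as depressed from 89 programs". With J = 89 to 95 and ICC = 0.02:

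| At risk | m = n/J | VIF | Correct SE / naive SE | True type I error |
|---|---|---|---|---|
| 995 | 10.5-11.2 | 1.19-1.20 | 1.09-1.10 | 7.2-7.4% |
| 408 | 4.3-4.6 | about 1.07 | 1.03-1.04 | about 5.8% |

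For example, 1 + (995/89 - 1) x 0.02 = 1.204, whose square root is 1.097, and 1.96/1.097 = 1.787 gives a two-sided 7.4%. At ICC 0 the ratio is 1.00 and the error is 5%.

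**4. Do the two effects occur together?** Step 3 assumes that the naive variance is otherwise correct. A null simulation checked this: 91 programs, ICC 0.02, wave hazards 20-40%, 3,000 runs per setting, no cluster correction.

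| n | Ties | Empirical SD / model SE | Rejection |
|---|---|---|---|
| 995 | Breslow | 0.89-0.99 | 2.3-4.4% |
| 995 | Efron | 1.10-1.11 | 7.3-7.9% |
| 408 | Breslow | 0.83-0.92 | 1.9-3.3% |
| 408 | Efron | 1.02-1.05 | 5.4-6.2% |

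A second simulation (90 programs, hazards 20-50%, 1,500 runs per setting, n = 995) gave rejection of 1.5-4.2% for Breslow and 6.3-9.9% for Efron. So where the effect shrinks, the standard error is already too large; where the standard error is too small, there is little shrinkage. At an ICC of 0.05, above the plan's range, the offset under Breslow fails: rejection is 5.7-7.9% for n = 995, against 10.8-12.9% for Efron.

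**The case against.** The strongest reply is that this is brevity in a one-paragraph summary of an exploratory analysis. The linear regression in the same paragraph and the 4-year logistic model also repeat no clustering statement, the text cites a publication for detail, and Section 5 commits to clustering for the whole design. Nor is the Cox framework as such unsuited to ties, since its exact-discrete form is built for them. Remission is also analysed as a count of periods and by logistic regression at 4 years.

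Most of this stands. A reader might infer that the hazard ratio is biased toward 1 and that its standard error is also too small. The documents do not support that: they name no tie method, so even the direction of any bias is unknown, and step 4 shows that the two faults come from different tie methods. A reader might also infer that clustering was dropped. The paragraph's silence does not show this, given the general commitment.

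The count of three waves is itself an inference. The remission definition includes the PHQ-2 criterion used at 4 years, so a fourth wave is possible; ties would still be heavy.

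The gap itself remains. The general commitment does not say how a Cox variance would be clustered, and nothing in the documents settles the tie method.

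**Conclusion.** The concern holds as a gap in specification with a better method available, not as a demonstrated error. On the same data, a true hazard ratio of 1.50 could be reported as about 1.29-1.42 (Breslow) or 1.47-1.50 (Efron) at assumed hazards of 20-50% per wave, or as about 1.59-1.71 (exact-discrete, an odds ratio) at 20-40%. At 10% per wave the spread narrows to 1.46-1.54.

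Over the plan's ICC range, ignoring programs under Efron would require the standard error to be multiplied by 1.00-1.10 for clinical remission, with type I error up to about 7.4% by the plan's formula and somewhat higher in some simulated settings. For community-defined remission the factor is 1.00-1.04, with type I error up to about 5.8%. Under Breslow the test is conservative at ICC 0.02 or below.

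These sizes rest on assumed wave hazards and hazard ratios, similar expected program sizes and no loss to follow-up. The analysis is exploratory, so no primary conclusion is affected. The point is a low-priority improvement.

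**What to change.** Replace each Cox model with a discrete-time hazard model: one record per client per wave at risk, complementary log-log link, one intercept per follow-up wave, and variance clustered on program. The intervention coefficient is still a log hazard ratio, and no tie method is needed. Keep the stated sequence of models (intervention alone, then social determinants, then depression treatment).

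State the horizon, and state which weighting and imputation approach applies. A reference to the other models would not settle the weighting: the 6-month analysis is weighted, whereas the 12-month repeated-measures and 3-year longitudinal analyses are not.

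If the Cox models are kept, name the tie method and the program-level variance estimator.

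The cost is one standard regression per remission definition on data already collected, and a sentence or two of text.

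### Community-defined remission was apparently already met at baseline by about 58–60% of clients enrolled for depression, so a difference on it is not by itself an effect on depression remission; the remission count also starts at baseline

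*Combined protocol and SAP*

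**What the plan says.** Appendix A, section A1 (Enrollment), sets the entry condition: "Study eligibility was limited to clients providing contact information and depressed based on a score of 10 or greater" on a modified PHQ-8.

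Section A4 (Exploratory analyses) defines two indicators:

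- Clinical remission is PHQ-8 below 10 or PHQ-2 below 3.
- Community-defined remission, developed with stakeholder input, is "PHQ-8 $<$ 10 or PHQ-2 $<$ 3 or MCS-12 $>$ 40 or any mental wellness". The wellness component needs only one of three items, which ask about frequency "in the previous 4 weeks to feeling calm or peaceful, having energy, or being happy".

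The indicators enter three analyses:

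- **Time to first remission.** Cox models start from the 1,018 clients with any survey data, "limited to those at risk for subsequent clinical (n = 995) and community-defined (n = 408) remission at baseline".
- **Periods in remission.** "We also used a count of survey periods in remission from baseline up to 3-year follow-up". Linear regression is applied to all 1,018. The text does not say which indicator is counted.
- **Four-year outcome.** Logistic regression is used for each indicator, with the baseline measure of the outcome among the covariates. No at-risk restriction is stated.

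Section 6 gives the reason for the 4-year survey: "additional follow-up of the 3-year sample was desired to show longer-term effects on depression remission".

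**The concern.** The community-defined indicator joins its criteria by 'or'. A client whose PHQ-8 is still 10 or more counts as remitted if MCS-12 exceeds 40 or one wellness item is endorsed often enough. In a sample selected for depressive symptoms, the at-risk counts suggest that most clients were in this state at the start.

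The risk of misreading is concrete. Section 6 reports that CEP, relative to RS, had already reduced poor mental health-related quality of life over 6–12 months, and it does not list depression among the improvements. Poor quality of life is defined there as MCS-12 of 40 or below, and its complement is one of the routes into community-defined remission. A known quality-of-life difference could therefore reappear as a remission difference with no change in depressive symptoms. The 4-year analysis names both indicators side by side as remission and does not say which carries the conclusion about depression.

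The count raises a separate issue. An outcome that includes the baseline wave contains a state recorded before any follow-up.

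**Working it through.** Inputs, all from Appendix A: full sample 1,018; at risk at baseline for clinical remission 995; at risk for community-defined remission 408 (A4); baseline interviews completed 981 (A1). The at-risk figures are reported counts, so no plan formula has to be reproduced. The check is what they imply.

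1. **Not at risk at baseline.** Community-defined: 1,018 − 408 = 610, and 610/1,018 = 59.9%. Clinical: 1,018 − 995 = 23, and 23/1,018 = 2.3%.

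2. **Route into the composite.** Everyone in clinical remission is also in community-defined remission, because the PHQ criteria are among the alternatives. So 995 − 408 = 587 clients were at risk for clinical remission but not for the community-defined kind. That is 587/610 = 96% of those not at risk and 587/995 = 59.0% of those not in clinical remission. The definition leaves them only MCS-12 or a wellness item as the route.

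3. **Sensitivity to the reason for exclusion.** The plan does not itemise reasons. If all 23 were excluded for some cause other than remission, the share is 587/1,018 = 57.7%.

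4. **Sensitivity to missing baseline interviews.** At least 1,018 − 981 = 37 clients had no baseline interview. If all 37 are among the 610, the share of those interviewed is 573/981 = 58.4%. If none is, it is 610/981 = 62.2%.

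5. **Whether the existing safeguards change what is measured.** The 408 in the Cox risk set failed every criterion at baseline, so an event among them is a real change of state. That change can still occur through MCS-12 or one wellness item with PHQ-8 at 10 or more. Adjusting the 4-year model for the baseline measure accounts for where clients started. It does not turn a wellness response into symptom remission.

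6. **The count.** The waves up to 3 years are baseline, 6, 12 and 36 months. Counting from baseline gives a maximum of 4, and counting from 6 months gives 3. With baseline included, up to 610 clients start with one period under the composite, or 23 under the clinical definition. To size the noise, assume equal arms of 509 and ignore clustering and weights. The standard error of the between-arm difference in the baseline term is √(2p(1 − p)/509).
   - Composite, p = 0.599: √(2 × 0.240/509) = 0.031, so chance differences of about ±0.06 of a period (1.96 × 0.031).
   - Clinical, p = 0.0226: √(2 × 0.0221/509) = 0.009, so about ±0.02 of a period.

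**The case against.** A reader might infer that the long-term follow-up cannot show an effect on depression remission. The documents do not support that. Clinical remission is a separate PHQ-based indicator with its own risk set of 995 and its own 4-year analysis, and it addresses the stated purpose directly.

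A reader might also take the loss of 60% of the sample from the community-defined Cox model as a defect. It is the correct risk set for time to first event.

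Nor do the documents establish that 587 clients were depressed and in remission at the same moment. Eligibility PHQ-8 was taken at the screener, and the baseline telephone survey came separately. A4 does not say which of them sets baseline PHQ status. If it was the screener, the PHQ and the other components may have been recorded at different times.

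The composite is also fully defined, credited to stakeholders, introduced under an exploratory heading, and consistent with the trial's declared interest in positive mental health. Tightening it to require the symptom criterion together with MCS-12 or wellness is tempting. But Appendix A reports these analyses in the past tense, so that would be a new outcome chosen after the data were known, replacing an agreed community definition.

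On the count, the arms are randomised, so a baseline credit adds noise and chance imbalance, not a systematic lean towards one arm.

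All of this stands. It narrows the point to interpretation and to the starting wave of the count. It does not answer the question of what the composite measures.

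**Conclusion.** The concern holds in limited form. About 58–60% of a sample enrolled for depressive symptoms had apparently already met community-defined remission at baseline, nearly all of them without clinical remission. A difference on the composite is therefore not, on its own, evidence of depression remission, and A4 should say which indicator carries that conclusion.

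The size rests on two assumptions: that clients outside a risk set were left out because they already met the indicator, and that screener-based or imputed status for clients without a baseline interview is acceptable. The alternatives checked above move the share only between 57.7% and 62.2%.

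The count problem depends on a literal reading of its starting point. Its size depends on the unstated choice of indicator, with up to 610 clients affected under one and 23 under the other.

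**What to change.** In Appendix A, section A4:

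- State that any conclusion about depression remission rests on the clinical, PHQ-based indicator already analysed. Because it would carry that weight, also reconcile the text that uses PHQ-2 below 3 both for depressive symptoms at 4 years and for remission.
- Keep community-defined remission as a separate community-prioritised outcome, and report it by component: PHQ, MCS-12 and wellness.
- Start the count of remission periods at the 6-month survey, enter baseline status as a covariate, and state which indicator is counted.
- State whether baseline PHQ status comes from the screener or from the baseline interview, and how clients without a baseline interview were classified.

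No new data are needed. The cost is some added reporting, a re-run of the count model, and one period fewer in the count.
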